## 5.2 Recruitment Methods

Site PIs will invite (e.g., in-person, email, service line notification, phone) local PCMH clinicians to participate in BBTI training. PCMH clinicians who agree to attend training, upon completion will be invited to participate in the study. The goal is to recruit at least 2 PCMH clinicians from each site. See Appendix 10.1 for phone and email recruitment scripts. PCMH clinicians at local sites may also become aware of the opportunity to participate through participating colleagues and/or through the BBTI training available through TMS. They may then contact their local Site PI/coordinator or coordinating study PI/coordinator to express interest in participating.

Veterans will not be recruited. Retrospective data collection from Veterans' electronic health records (e.g., CPRS, CDW) will be used to obtain variables of interest related to Veteran treatment outcomes and variables related to PCMH clinician delivery of BBTI (or CBT-I). Our goal is to obtain retrospective data from at least n=329 Veterans, which would represent approximately 0.75% of unique Primary Care patients with insomnia across all four participating sites; this would result in 90% power for the Reach variable in RE-AIM (see Table 5 for full power analysis [section 5.6]).

There will be no participant payments.

### **5.3 Informed Consent Procedures**

VA employee participants—site PIs and PCMH clinician—will be invited to participate in this trial (see section 5.4). Those who volunteer to participate will complete a verbal informed consent by phone, administered by study staff at the hub site in Pittsburgh. See Appendix 10.2 for the study information sheet that will be provided to all potential participants prior to consent. We are requesting a waiver of documentation of informed consent to conduct the consent process by phone. VA employee participants will be informed that audio-recorded interviews are involved and consent for audio-recording will be documented along with their consent to participate in the study. During the interviews, immediately after recording begins, study staff will ask all participants if they agree to being recorded. If not agreeable with recording, the recording will stop, but the interview will still proceed. This agreement/disagreement will be documented by study staff and stored in the study network drive where audio-recordings are stored. Other than their name, no other PHI will be collected from VA employee participants.

We will collect retrospective data, from the electronic medical records, for Veterans who receive BBTI from PCMH clinician at the participating sites. No information will be collected directly from Veterans; a waiver of informed consent and a waiver of HIPAA will be requested. Veterans will be receiving usual care (BBTI), thus, the risk to Veterans is minimal and limited to breach of confidentiality from the retrospectively collected data.

Study staff at the hub site and participating sites will complete and stay up to date on the required trainings for the conduct of human subjects research.

### **5.4 Inclusion/Exclusion Criteria**

Site PIs and PCMH clinician are the focus of this study with retrospective data collection for Veterans who receive BBTI (or CBT-I) delivered by PCMH clinician at the participating sites. Each participating site PI will be invited to participate in this study. PCMH clinician at each participating site will be invited, by their site PI, to attend a training for BBTI. Those who attend and complete BBTI training will be invited to participate in this study. PCMH clinician who have been previously training in CBT-I will not be required to take the BBTI training as BBTI is adapted from CBT-I and there is significant overlap. Women and minorities will be included in this study.

There will be retrospective data collection from electronic health records and databases for Veterans who receive care in PCMH and engage in BBTI (or CBT-I) from a PCMH clinician.

### **5.5 Study Evaluations**

**Data Collection and Outcomes by Specific Aim.** Data collection will be accomplished through three mechanisms: (1) Reach, Effectiveness, Adoption, Implementation, and Maintenance (RE-AIM) outcomes will be retrospective, based on custom queries of electronic health record data through the VA Corporate Data Warehouse (CDW); (2) CFIR-guided qualitative interviews, conducted with site PIs and PCMH clinician, to assess their perspectives on BBTI training and the implementation process; and (3) surveys, completed by site PIs and PCMH clinician, on utilization of implementation strategies.

**Specific Aim 1:** To test the impact of BBTI+IS to improve RE-AIM outcomes and the sustainable delivery of BBTI without implementation support.

**RE-AIM Implementation Outcomes.** These outcomes will be measured with data from electronic health records through custom queries of tables in the CDW. Extracting information from Veterans' progress notes, including a custom BBTI templated note (see Appendix), will allow for data collection and organization to calculate RE-AIM outcomes, operationally defined below. The data query will be regularly conducted (e.g., weekly) to allow for frequent updates of the outcomes. Data queries that extract variables of interest from progress notes, such as the ISI scores, have been successfully tested as part of the PI's pilot project on characterizing insomnia care in the VA. Variables necessary to calculate RE-AIM will be measured during all phases (pre, implementation, and post). This data organization will help facilitate analyses and comparisons across sites at

similar phases and across sites for similar phase comparisons. It will also allow for within site comparisons to evaluate the impact from pre- to implementation, from implementation to post-implementation, as well as the evaluation of long-term sustainability (>6-months post-implementation). SQL Server queries will be utilized to automatically update the data reported in the study's Microsoft Access database. The Access database front-end will be comprised of a form with buttons for on-demand updates to results from the existing queries (e.g., ISI scores from progress notes). Also, we will closely monitor the ongoing electronic health record update to Cerner. While the Cerner integration is not expected to impact this study, if participating sites do integrate Cerner during the study period, we will adapt our automated data query methods or utilize a standardized chart review form to collect data from individual Veteran records.

Reach, the primary outcome, will calculate the number of Veterans in PCMH who receive insomnia-related care. This may include (1) Veterans in Primary Care/PCMH clinics who receive an insomnia diagnostic code and/or a sedative hypnotic medication (see Table 4); (2) Veterans in Primary Care/PCMH clinics who initiate BBTI or CBT-I (indicated by a relevant progress note/encounter); (3) the proportion of Veterans in Primary Care/PCMH clinics who initiate BBTI/CBT-I relative to the Veterans in Primary Care/PCMH clinics who are eligible to initiate BBTI/CBT-I. Data collection will begin 1/1/2020 in order to compare to data during the study period (beginning 1/1/2021) and evaluate change. While the focus is on BBTI, initiation and engagement in CBT-I is also relevant as it will be important to evaluate different insomnia services delivered in Primary Care/PCMH (e.g., diagnoses, medications, BBTI, CBT-I).

Tracking these insomnia-related variables will allow us to measure trends in treatment initiation, diagnosis, and prescribing practices at different stages of the study (and prior to the study). However, this will still likely represent an underestimate of potential Reach since there will be Veterans with insomnia who turn down a PCMH visit, do not receive an insomnia diagnosis, and decline a sedative-hypnotic.

Table 4. Insomnia diagnoses and prescription sedative-hypnotics eligible for Reach denominator.

|                    |            |                                                                                                                  |
|--------------------|------------|------------------------------------------------------------------------------------------------------------------|
| Diagnoses          | ICD-10:    | F51.0, F51.01, F51.02, F51.03, F51.04, F51.05, F51.09, G47.00, G47.01, G47.09                                    |
|                    | ICD-9:     | 307.41, 307.42, 780.50, 780.51, 780.52                                                                           |
| Sedative-hypnotics | On label:  | diphenhydramine, doxepin, eszopiclone, prazosin, ramelteon, suvorexant, temazepam, triazolam, zaleplon, zolpidem |
|                    | Off label: | hydroxyzine, melatonin, trazodone, others specifically indicated for sleep                                       |

Effectiveness will be measured as the change on the ISI from the initial score obtained (e.g., PCMH initial evaluation, BBTI/CBT-I session 1) to the last BBTI/CBT-I session. The ISI is commonly used within the VA and is easily accessible within VA electronic health records through the Mental Health Assistant toolbox as well as Behavioral Health Lab software, which was developed for use in PCMH. ISI data may also be extracted from CPRS progress notes (e.g., BBTI progress notes). The ISI has well-established psychometrics with good reliability and validity. It is standard practice as part of insomnia-related treatment (i.e., BBTI and CBT-I) and PCMH treatment (e.g., depression, anxiety, pain) to use measurement-based care (e.g., ISI, PHQ-9) and include outcome measures in progress notes to inform care and track treatment progress. For Effectiveness to be calculated, ISI scores from each BBTI/CBT-I session (e.g., entered in a BBTI progress note or CBT-I templated note) by PCMH clinicians will be extracted through the automated CDW queries to calculate outcomes for each Veteran. Rates of treatment response and remission will also be calculated. Response is a reduction of ≥8 points on the ISI from pre- to post-treatment. Remission is achieving a post-treatment response and an ISI <8. Previous BBTI trials found treatment response rates of 42-77% and remission rates of 28-53%.

Adoption will be measured in two ways: (1) the number of PCMH clinicians who undergo training in BBTI relative to the number of PCMH clinicians eligible for training; and (2) the number of PCMH clinicians who treat at least one Veteran with BBTI relative to the total number of PCMH clinicians trained.

Implementation, or treatment fidelity, will be measured by rating mock treatment sessions with enrolled PCMH clinicians; ratings will be completed by site PIs using the BBTI-CRS. All enrolled PCMH clinicians will be rated following BBTI training, and then quarterly thereafter. They will receive clinical feedback by their site PI, as needed, and, if they score below the competency cutoff (<50% or <2 per item; 2=satisfactory), any necessary re-training from their site PI. If PCMH clinicians pass three consecutive mock sessions, they have the option of

discontinuing the mock sessions until mock session ratings at the end of the implementation phase and the end of the post-implementation phase. The BBTI-CRS scores will be used to develop an “implementation score” for each site—the average ratings across each site’s enrolled PCMHI clinicians.

As a secondary measure of Implementation, all enrolled PCMHI clinicians will have a random selection of BBTI progress notes reviewed, by their site PI, to assess BBTI elements being utilized (10% or at least 1 per month of eligible notes). Clinicians who neglect important BBTI elements (e.g., discuss 4 rules, assess with ISI, titrate TIB) will receive clinical feedback from their site PI. Each site’s secondary “implementation score” will be the average number of important elements across enrolled PCMHI clinicians reviewed progress notes. Though previous trials of BBTI have used audio-recorded sessions to measure Implementation, feedback from clinicians (current and prior studies) has suggested that audio-recording sessions were considered intrusive to delivering clinical care and limited rapport building with Veterans.

While not recording sessions is a less precise measure of Implementation/treatment fidelity, recorded sessions from the PI’s CDA found that clinicians consistently delivered treatment with competency (cutoff >50%; session 1 M=78% [SD=13%]; session 3 M=94% [SD=5%]) and only one rated session for a single clinician was below the 50% cutoff (47.5%).

Maintenance will measure the sustainability of Reach, Effectiveness, Adoption, and Implementation during the 6-month post-implementation phase as well as during the long-term sustainability period (>6-months). The outcomes from the sustainability periods will then be compared to the outcomes during the pre- and implementation phases. The same operational definitions as described above will be used for Reach, Effectiveness, and Implementation. For Adoption, comparisons will be based on the rate a clinician delivers BBTI over time within each study phase. For example, the number months a PCMHI clinician Adopts BBTI (i.e., delivers BBTI to a Veteran) relative to the number of months [n=6] in the post-implementation phase.

Specific Aim 2: To identify specific strategies that help promote the implementation of BBTI in PCMHI using qualitative interviews and utilization surveys.

Qualitative and Survey Outcomes. CFIR-guided interviews will be conducted with site PIs and 2-3 PCMHI clinicians per site (n=9-12/site; n=36-48 across all sites) at three time points: after BBTI training (study month 3); at the end of the 12-month implementation phase; and at the end of the 6-month post-implementation phase. Interviews will be recorded (if the participant is willing) utilizing any of the VA-approved recording options available during the study period (i.e., VA phone, Phillips recorder, and Microsoft Teams [approved methods at time of this submission]). Interviews will be guided by CFIR^63 but will not follow a script verbatim; rather, the interview guide (see Appendix) will be treated as a loose structure to assist the interviewer, , a masters- and/or doctoral-level qualitative staff member at the coordinating site who is not involved the implementation process. This will help ensure confidentiality of the data for the site PIs and PCMHI clinicians who engage in the qualitative interviews. The first interview will focus on the BBTI training experience and anticipated barriers and facilitators that may impact implementation efforts. The second will focus on site PI and PCMHI clinician experiences during the implementation phase and how the access to, and support for, the bundle of strategies influenced their ability to deliver BBTI in PCMHI, specific strategies that were helpful (or not), and barriers that may continue to impede implementation efforts. The final interview will focus on issues of sustainability and experiences delivering BBTI during the post-implementation phase. Interviews will help to provide context for the implementation process and to better differentiate sites on strategies that worked (or not).

During the implementation and post-implementation phases, site PIs and enrolled PCMHI clinicians will complete a quarterly survey (n≥12 surveys/site, n≥48 surveys across all sites) about strategies from the bundle proposed (e.g., “Did providers use X strategy to promote delivery of BBTI?”). These surveys will assess the uptake of strategies, longitudinally, across study phases. Site PIs and PCMHI clinicians will also be asked to rate each strategy on its importance during the last three months (i.e., how vital a strategy was to improving implementation) and its feasibility during that time (i.e., how possible a strategy was to implement). The surveys will be managed through Microsoft Forms by the study coordinator at the coordinating site .

Each enrolled site PI and PCMHI clinicians will also be asked to complete a demographics form through Microsoft Forms after verbal consent.

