| 
CFIR: Learning climate
                                                           | 
Example: Site PIs will meet regularly with their local PCMH clinicians (e.g., monthly by phone) to discuss implementation efforts, both successes and setbacks. They will also engage with local clinical stakeholders (i.e., Primary Care teams). Also, during scheduled and ad hoc calls, external facilitators at the coordinating site will provide guidance regarding barriers towards implementation and work with site PIs to reinforce successful strategies with their local PCMH clinicians.
                                                                                                                                                                                                                                      |
| 
6.
ERIC: Increase demand with marketing to patients
                          | 
Marketing to Veterans can increase awareness, referrals, and same-day access of BBTI in PCMH. Potential methods to be used: (1) letters mailed directly to Veterans prior to upcoming Primary Care appointments; and (2) signs, brochures, and other educational information in Primary Care clinics regarding BBTI services and encouraging Veterans to discuss sleep issues with their Primary Care team; (3) digital educational products (e.g., short video) that can be shown to Veterans by providers and/or posted on VA websites (e.g., Facebook, YouTube). The process of identifying Veterans prior to appointments, and the creation of marketing materials, will be managed by the coordinating site and executed locally by site PIs.
 |
| 
CFIR: Peer pressure
                                                              | 
Example: The coordinating site will identify Veterans with an insomnia diagnosis and/or prescription for a sedative-hypnotic medication who have a Primary Care appointment in the next month. This information will be forwarded to site PIs, who can then mail information to these Veterans about BBTI in Primary Care and encourage them to discuss sleep-related problems with their PCP.
                                                                                                                                                                                                                                                                                                                                              |

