## 5.6 Data Analysis

Specific Aim 1: To test the impact of BBTI+IS to improve RE-AIM outcomes and the sustainable delivery of BBTI without implementation support.

**Analyses.** Power estimates were based on Reach and were conducted for an incomplete stepped-wedge design with four steps (four participating sites) with site randomization every six months. An incomplete design was used since the implementation phase stops after 12-months rather than continuing until study completion. Using VA 2018 data from Primary Care and PCMHI dashboards as estimates, all Primary Care patients at the four sites, n=99,572, are considered the potential sample (denominator). The pre-implementation phase sample are Veterans seen for same-day PCMHI care across the four sites, n=4,778 (numerator). Considering the prevalence of insomnia is estimated as 44% of Primary Care patients, n=43,812, and there is minimal insomnia care being conducted in PCMHI currently, we expect to increase overall PCMHI care even if only a fraction of Veterans with insomnia can be reached through the implementation intervention (BBTI+IS). If 0.75% of the estimated 44% with insomnia are seen in PCMHI (n=329, n≈82/site, 1-2 new Veterans per week/site) we have 90% power to detect a significant increase of 6.88% in PCMHI care (4,778 to 5,107) from pre- to implementation phase. See Table 5 for power estimates at different levels of Reach.

Table 5. Power estimates for Reach.

|                          | % of unique Primary Care patients with insomnia (n=43,812) |        |        |        |        |        |          |
|--------------------------|------------------------------------------------------------|--------|--------|--------|--------|--------|----------|
|                          | 2%                                                         | 1.5%   | 1.25%  | 1%     | 0.75%  | 0.5%   | Baseline |
| New PCMHI patients       | 876                                                        | 657    | 548    | 438    | 329    | 219    | --       |
| Current same-day access  | 5,654                                                      | 5,435  | 5,326  | 5,216  | 5,107  | 4,997  | 4,778    |
| Current PC patients      | 99,572                                                     | 99,572 | 99,572 | 99,572 | 99,572 | 99,572 | 99,572   |

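### The primary Reach outcome is not fixed to one measure, and the 90% power attributed to it was computed for same-day PCMHI care, which is none of the measures listed

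*Combined protocol and SAP*

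**What the plan says.** Section 5.5 opens with a count: "Reach, the primary outcome, will calculate the number of Veterans in PCMH who receive insomnia-related care". It then says what this might consist of:

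- Item 1: "This may include (1) Veterans in Primary Care/PCMH clinics who receive an insomnia diagnostic code and/or a sedative hypnotic medication (see Table 4").
- Item 2: "2) Veterans in Primary Care/PCMH clinics who initiate BBTI or CBT-I (indicated by a relevant progress note/encounter").
- Item 3: "the proportion of Veterans in Primary Care/PCMH clinics who initiate BBTI/CBT-I relative to the Veterans in Primary Care/PCMH clinics who are eligible" to start.

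Table 4, which item 1 cites for care received, carries the title "Insomnia diagnoses and prescription sedative-hypnotics eligible for Reach denominator". Aim 1 in section 3.1 repeats only the general idea of insomnia-related care, and the model paragraph in section 5.6 names no specific Reach variable.

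On power, section 5.2 attributes 90% to the Reach variable and refers to Table 5. Section 5.6 takes all 99,572 Primary Care patients as the denominator and describes the baseline thus: "The pre-implementation phase sample are Veterans seen for same-day PCMHI care across the four sites, n=4,778 (numerator"). The same paragraph states that "there is minimal insomnia care being conducted in PCMHI currently" and expects overall PCMHI care to rise.

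**The concern.** A primary outcome has to be one variable. Here it could be either of two counts or a proportion, and no composite, hierarchy or choice is given. The measures can also move differently under the same intervention. The marketing example in Table 3 (section 5.1) starts from Veterans who are already coded or medicated: "The coordinating site will identify Veterans with an insomnia diagnosis and/or prescription for a sedative-hypnotic medication". Success with that group shows up in items 2 and 3 but not in a count of unique Veterans under item 1.

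The only power statement for the primary outcome is also tied to a different variable. If the 90% does not belong to Reach, the study has no stated power for its primary comparison of pre-implementation with implementation.

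**Working it through.** **1. The plan's own inputs (section 5.6).** 0.44 × 99,572 = 43,812 with insomnia. 0.0075 × 43,812 = 329. 4,778 + 329 = 5,107. 4,778/99,572 = 4.80% and 5,107/99,572 = 5.13%. The relative rise is 329/4,778 = 6.89% (plan: 6.88%).

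**2. The plan's power.** Alpha, sidedness, ICC and cluster-period size are not stated, so I assume two-sided 0.05 and start with an unclustered two-proportion test, n = 99,572 per period:

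power = Φ[(p2 − p1)/SE − 1.96], with p2 − p1 = 0.003304 and SE = 0.000973 (pooled and unpooled agree to this precision).

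0.003304/0.000973 ≈ 3.39; 3.39 − 1.96 = 1.43; Φ(1.43) = 92.4%, against 90.03% in Table 5. For +219 the test gives 62.2%, against 59.25%. Some stepped-wedge settings come within one point of the plan at +219, +329, +438 and +548. One example, with about 99,572/8 patients per site per six months and a small ICC, gives 58.7%, 90.3%, 99.1% and 99.97%. These were found by searching over unstated inputs. They make 90% plausible for 4,778 to 5,107 but do not confirm it. All of them use 4,778/99,572 as the baseline.

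**3. What was powered, beside what was listed.**

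| Quantity | Numerator | Denominator | Baseline in the documents |
|---|---|---|---|
| Powered (5.6) | Veterans seen for same-day PCMHI care | All Primary Care patients, 99,572 | 4,778 |
| Item 1 (5.5) | Veterans with an insomnia code and/or hypnotic | None (count) | None |
| Item 2 (5.5) | BBTI/CBT-I starters | None (count) | None |
| Item 3 (5.5) | BBTI/CBT-I starters | Eligible Veterans | None |

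**4. The measures respond differently.**

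| Event | Item 1 (unique Veterans) | Item 2 | Item 3 (Table 4 as denominator) |
|---|---|---|---|
| More coding or prescribing, no new starts | Rises | Unchanged | Falls |
| BBTI start in a Veteran already coded or medicated | Unchanged | Rises | Rises |

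**5. Does 90% carry over?** Baselines here are assumptions. The same +329 and the same unclustered test as in step 2 give:

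- Item 1 as a share of 99,572: 68% at a 10% baseline, 54% at 15%, 45% at 20%. At 4.8% it is 92%, and it is higher below that.
- Item 2 over 99,572, baseline 50 to 500 starts: above 99.9%.
- Item 3 with 43,812 standing in for the eligible group: 99.9% at a 5% baseline, 95.4% at 10%.

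Allowing for extra variation changes the picture again. Take a rate of starts compared within sites 2 to 4 at their actual phase lengths, +329 per year over four sites, and an assumed overdispersion factor of 5 to 10. Power is 99.9% to 95.5% at an assumed 50 starts per year before implementation, and 92.3% to 66.8% at 500. With fixed site and calendar-period effects, all four sites and five six-month periods (no post-implementation data), the same inputs give about 91% to 64% and 41% to 23%.

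**6. Time base.** Under section 5.1, pre-implementation lasts 0, 6, 12 or 18 months by site and implementation lasts 12. Section 5.5 sets no interval over which Reach is counted.

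**The case against.** The strongest reply is that the three items are not rivals. Item 1 with Table 4 can be read as the denominator, item 2 as the numerator and item 3 as their ratio. The title of Table 4 supports this. So does the remark after the list that the tracked variables will underestimate potential Reach because some Veterans receive no visit, code or drug. This reading is reasonable and makes item 3 a natural candidate. But the text does not say it: Reach is introduced as a number, and item 1 is offered as something Reach may include.

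On power, the dashboard figures are openly used as estimates, and the added 329 are Veterans with insomnia newly seen in PCMHI, so the powered quantity is related to Reach. That stands. It does not give 4,778 an insomnia meaning, since the plan itself calls current insomnia care in PCMHI minimal. That 4,778 covers visits for any reason is an inference from the absence of an insomnia restriction.

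A reader might infer more than the documents support:

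- *That a raw count would be a third higher in implementation with no effect (48 against 36 site-months).* That excess comes entirely from site 1, which has no pre-implementation time. Sites 2 to 4 have 6 + 12 + 18 = 36 months against 3 × 12 = 36. Nor does the plan say that raw phase totals are compared: section 5.6 specifies mixed models, and Table 5 uses percentages.
- *That the measure will be picked after the results are seen.* The regular data queries also serve audit and feedback, and nothing shows such an intent.

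**Conclusion.** The point holds in two parts. The primary Reach measure is not fixed, and the 90% power belongs to another quantity. Both follow from the text without any assumption.

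The size of the power error cannot be stated. The range in step 5 of the working rests on assumed baselines, an assumed two-sided 0.05 and, in places, an assumed overdispersion. It shows only that the answer depends on the measure, the baseline and the model. It would be tempting to conclude that 90% is too high for item 1 and too low for starts. The documents do not support either direction: item 1 at or below 4.8% gives at least 92% on the simple test, and starts can fall well below 90% once extra variation or period effects enter. Nor is this a finding that 90% was miscalculated for same-day PCMHI care. This should be corrected before Reach is compared by phase.

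**What to change.** Before outcomes are compared by phase:

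- In section 5.5, name one primary Reach measure based on BBTI/CBT-I initiation. Either item 3, with Table 4 stated to be its denominator, or item 2 expressed as a rate would do. Item 3 follows the title of Table 4.
- Define it per fixed calendar interval (for example, monthly) by site, because pre-implementation time differs by site.
- Make the remaining measures secondary, and give Table 4 one role.
- In sections 5.2 and 5.6, stop attributing the 90% to Reach. Label it and Table 5 as power for same-day PCMHI care among Primary Care patients.
- Restate power for the named measure over a range of assumed baselines, with alpha, ICC and the analysis model stated.

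The cost is protocol wording and one new power calculation; the initiation data are already to be extracted. There are two real downsides. Care consisting only of a diagnosis or a drug leaves the primary outcome, which narrows the insomnia-related care named in Aim 1. The restated power may also turn out below 90%.
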